Aim 1: To examine whether high levels of estradiol augment the effect of THC on subjective anxiety, heart rate, blood pressure and salivary cortisol in females. To test this, female occasional cannabis users will receive a single dose of THC (0, 15 mg) during either the early follicular phase (days 1-8) when estradiol levels are low, or during the late follicular phase (days 9-14) when estradiol levels are high. Participants will attend two experimental sessions separated by at least four days, to allow for clearance of the drug. Plasma levels of estradiol, progesterone, and endocannabinoids, as well as salivary cortisol, physiological measures and subjective mood ratings will be obtained at the beginning of all three sessions. During the sessions, physiological measures, subjective ratings of drug effects and mood, and salivary cortisol will be obtained at regular intervals after drug consumption. I hypothesize THC will produce a greater increase in subjective anxiety, heart rate, blood pressure and salivary cortisol during the late follicular phase, and that this will be correlated with higher circulating levels of estradiol.

Aim 2: To examine whether low levels of circulating endocannabinoids augment the effects of THC on subjective anxiety, heart rate, blood pressure and salivary cortisol in females. To test this, the plasma samples mentioned above will also be analyzed for endocannabinoids, anandamide (AEA) and 2-arachidonoylglycerol (2-AG) levels. Baseline AEA and 2-AG levels will be compared to THC-induced increases in subjective anxiety, heart rate, blood pressure and salivary cortisol. I hypothesize females with lower endocannabinoid levels will exhibit greater THC-induced increases in subjective anxiety, heart rate, blood pressure and salivary cortisol levels.

Aim 3: To evaluate determine whether subjective anxiety mediates the physiological stress response after THC. To test this, I will use a multilevel longitudinal mediation model to analyze the collected data. Our independent variables will include within-subjects drug dose and between subjects estradiol (EFG or LFG), AEA and 2-AG levels. Our mediator variable will be subjective anxiety across session time. Our dependent outcome measures include heart rate, blood pressure and salivary cortisol across session time. A multilevel

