For this study we will use a mixed within- and between subject design to examine effects of THC (0 and 15 mg) in two groups of female occasional cannabis users: women tested in the early follicular phase of their menstrual cycle (EFG; N=30) and women tested in the late follicular phase (LFG; N=30). Occasional cannabis users will be defined as individuals who have used cannabis 10 or less occasions in the past thirty days. Females will be randomly assigned EFG or LFG groups. EFG women will be tested 1 to 8 days since the first day of menstruation and LFG women between days 9 and 14. Subjects will attend two four-hour experimental sessions in which they receive THC (15 mg THC) or placebo in counterbalanced order under double blind conditions. Plasma and saliva samples will be obtained before capsule consumption at the start of each session for baseline hormone, endocannabinoid and cortisol levels. The primary outcome measure is salivary cortisol, which will be measured both at baseline and periodically post-drug consumption. Secondary outcome measures include heart rate, blood pressure, body temperature, subjective drug effects (i.e. "feel drug effect"), and THC-induced anxiety. For Aim 1 we will examine THC-induced increases in cortisol in relation to baseline estradiol levels. For Aim 2 will examine THC-induced cortisol in relation to baseline endocannabinoid levels. For Aim 3 we will examine THC-induced increases in heart rate and subjective drug effects relative to THC-

induced increases in cortisol. The study will be approved by the Institutional Review Board at the University of Chicago, in accordance with the Code of Federal Regulations (Title 45, Part 46) adopted by the National Institutes of Health and the Office for Protection from Research Risks of the US Federal Government. The studies will be conducted in accordance with the Helsinki Declaration of 1964 (revised 1989) and the National Advisory Council on Drug Abuse Recommended Guidelines for the Administration of Drugs to Human Subjects.

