Orientation Session Participants will first participate in a 1-hour orientation session to provide informed consent, agree to the study conditions described above, complete the Trait Anxiety Inventory (Spielberger et al. 1971) and the Anxiety Sensitivity Inventory (Reiss et al. 1986), and practice questionnaires that will be administered throughout the sessions. Participants will be instructed to refrain from any use of drugs or alcohol for 24 before the experimental sessions. They will be advised that they must pass urine tests on the days of their experimental sessions for recent drug use including cannabis, and to pass these tests they should abstain from use for one week if they are light users (1-2 times per week) and for two weeks if they are heavier users (e.g., every other day). They will be told to have a normal night's sleep before the session and abstain from eating for at least 6 hours prior to their session. For blinding purposes, subjects will be told the capsules used in the study may contain a placebo, stimulant, cannabinoid-like drug, or sedative. The reason for blinding is we wish to study the pharmacological effects of this drug, without the possible confound of expectancies. We and others have shown that expectancies influence responses to drugs, in ways that might obscure true biological differences in the effects of the drug (see Mitchell et al. 1996; Kirk et al. 1998; Metrik et al. 2009; Heinz et al. 2013). Subjects will then practice the physiological measures and subjective questionnaires.

Experimental Session Timeline Participants will attend two experimental sessions lasting from 12:00 pm to 4:00 pm. Sessions are run from 12:00 pm to 4:00 pm to account for the diurnal rhythm of salivary cortisol—levels reach lowest levels at around midnight, start to rise at around 2:00 am to 3:00 am, reach a peak at around 8:30 am, and then slowly decrease back down to complete the cycle over 24 hours (Debono et al. 2009). Females in EFG will participate 1-8 days after first day of menstruation, at a time when both estradiol and progesterone levels are low (Barbieri et al. 2014). Females in the LFG will participate 9-14 days after first day of menstruation, at a time when estradiol levels are peaking or have just peaked, but progesterone levels remain low. The half-life of oral THC in infrequent users is about 1.3 days (Smith-Kielland et al. 1999). Therefore sessions will be scheduled with a minimum of 4 days to allow for washout.

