Statistical Analyses Sample Size Calculation: Sample size calculations were conducted using G*Power3.1 Software. Since there are no published data on effects of estradiol or eCB levels on response to THC a small effect size was assumed ($d = 0.3$). Recruiting 30 participants for each experimental group, 30 females in early follicular phase, 30 females in late follicular phase, for this study will allow for 80% power to detect an effect at alpha level $p = 0.05$.

A multilevel longitudinal mediation model will be used to analyze the collected data. Our independent variables include within-subjects drug dose and between subjects estradiol (EFG or LFG), AEA and 2-AG levels. Our mediator variable is subjective anxiety across session time. Our dependent outcome measures include heart rate, blood pressure and salivary cortisol across session time. A multilevel longitudinal mediation model will allow for the determination of how drug condition and baseline estradiol, AEA and 2-AG levels affects subjective anxiety across session time, which mediates changes in heart rate, blood pressure and salivary cortisol.

Expected Outcomes Based on several preclinical studies, I expect the LFG to have higher levels of estradiol and anandamide at baseline than the EFG, but no significant differences in baseline trait anxiety, anxiety sensitivity or salivary cortisol (Reed and Carr, 2000; Gorzalka and Dang, 2012; Monero-Lopez et al. 2018). Further, I expect that the effect of THC on subjective anxiety, heart rate and salivary cortisol will be greater in the LFG compared to the EFG, even after including any possible baseline differences in cortisol, trait anxiety or endocannabinoids as a covariate. Additionally, based on preliminary data and prior literature, I expect females with lower endocannabinoid levels, after controlling for cycle phase or estradiol levels, to experience larger increases in subjective anxiety, heart rate and report significantly greater subjective drug and mood effects of oral THC in a dose dependent manner (Hill et al. 2010). Finally, I expect THC-induced change in cortisol to mediate the increase in heart rate and greater subjective drug and mood effects. These results will contribute significantly to the small literature on individual differences in response to THC and lay a foundation for future

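### Does the plan need to say which session's endocannabinoid or estradiol value moderates the response to THC?

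*Combined protocol and SAP*

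**What the plan says.** Statistical Analyses names the model terms: "Our independent variables include within-subjects drug dose and between subjects estradiol (EFG or LFG), AEA and 2-AG levels". Here estradiol is the phase group, and AEA and 2-AG are measured levels, all entered between subjects. Later in the same paragraph the model is described with estradiol as a baseline level.

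The Approach section schedules the blood draws: "Plasma and saliva samples will be obtained before capsule consumption at the start of each session for baseline hormone, endocannabinoid and cortisol levels". With two sessions, each woman has two values of every analyte. (One sentence in Aim 1 mentions three sessions. Every other description of the design has two, so this is a clerical slip.)

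Aim 2 says: "Baseline AEA and 2-AG levels will be compared to THC-induced increases in subjective anxiety, heart rate, blood pressure and salivary cortisol". It does not name the session. The Approach section words Aim 1 by level: "For Aim 1 we will examine THC-induced increases in cortisol in relation to baseline estradiol levels". Expected Outcomes predicts the endocannabinoid effect "after controlling for cycle phase or estradiol levels".

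On timing, the Approach section says: "EFG women will be tested 1 to 8 days since the first day of menstruation and LFG women between days 9 and 14". Experimental Session Timeline adds: "Therefore sessions will be scheduled with a minimum of 4 days to allow for washout". It describes the late follicular window as "at a time when estradiol levels are peaking or have just peaked".

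**The concern.** A between-subject moderator needs one value per woman, and the plan collects two without a rule for combining or choosing them. The candidates are the first-session value, the THC-session value, the two-session mean, or each session's own value.

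These need not agree. If both sessions fall in one cycle, which the documents do not state, the four-day gap leaves few late follicular day pairs, all running from day 9 or 10 to day 13 or 14. Estradiol may well move over that interval.

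One candidate carries a known hazard. Suppose a level affects the post-capsule outcome to the same degree under THC and placebo. The THC-minus-placebo response then contains the difference between the two session levels, and regressing it on the THC-session level yields a slope without any augmentation. A negative common slope for AEA or 2-AG, or a positive one for estradiol, would imitate what Aims 2 and 1 predict.

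Two further points add to the unease: the drug-by-moderator terms are not written out, and estradiol could be tested as both label and level.

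**Working it through.** **Inputs from the documents.** 60 women (30 per phase group), two sessions in counterbalanced order, a gap of at least 4 days, windows of days 1-8 and 9-14, and a THC half-life of 1.3 days. The plan gives no figure of its own on this point to reproduce.

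**Assumed inputs, not in the documents.** Common slope beta = -0.3 SD per SD; between-session correlation of the level r = 0.4 to 0.8; between-session correlation of the residuals rho = 0.3 to 0.8; all variances 1.

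**Day pairs at least 4 days apart within one cycle.** Days 1-8: 10 of 28. Days 9-14: 3 of 15, namely 9/13, 9/14 and 10/14.

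**False slope with no augmentation.** Let L_T and L_P be the levels at the THC and placebo sessions, and D the THC-minus-placebo response.

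D = beta(L_T - L_P) + (e_T - e_P)

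- *THC-session value.* cov(D, L_T) = beta(1 - r), so the slope is -0.3 x 0.6 = -0.18 at r = 0.4, -0.3 x 0.4 = -0.12 at r = 0.6, and -0.3 x 0.2 = -0.06 at r = 0.8.
- *Two-session mean M.* cov(L_T - L_P, M) = (1 - 1)/2 = 0, so the slope is 0.
- *First-session value.* It is L_T in half the women, with slope beta(1 - r), and L_P in the other half, with slope -beta(1 - r). Counterbalancing averages these to 0.
- *Each session's own value, with subject effects and a drug-by-level term gamma.* D has terms b(L_T - L_P) + gamma L_T. Since L_T = M + (L_T - L_P)/2, this equals gamma M + (b + gamma/2)(L_T - L_P). It is the same test as mean plus between-session difference, and is unbiased.

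**Simulated false-positive rate at nominal 5%** (n = 60, order term included):

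| Moderator value | r = 0.4 | r = 0.6 | r = 0.8 |
|---|---|---|---|
| THC-session (rho 0.3 / 0.5 / 0.8) | 20 / 25 / 51% | 12 / 14 / 27% | 6 / 7 / 10% |
| First-session | 4-6% | 4-6% | 4-6% |
| Two-session mean | about 5% | about 5% | about 5% |
| Own-session with subject effects | 4-6% | 4-6% | 4-6% |

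**When the hazard disappears.** The session-to-session part of the level must itself drive the outcome. If the association lies only between women, the THC-session value also gives 4.7-5.2%. If the level effect is fully present before the capsule and cancels in change from baseline, every rule gives about 5%.

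**Power depends on the assumed mechanism.** True augmentation of -0.3, r = 0.6, no common slope, rho 0.3 / 0.5 / 0.8:

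- Acting through the woman's mean level: the THC-session value has slope -0.3 x (1 + 0.6)/2 = -0.24 and power 33 / 43 / 79%; mean plus difference has -0.30 and 40 / 51 / 87%.
- Acting through the THC-day level: both slopes are -0.30; power is about 48 / 60 / 93% for the THC-session value and 39 / 50 / 87% for mean plus difference. The ranking reverses.

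**Estradiol as label and level.** With the two tests correlated 0.5 to 0.8, counting either as success gives a null error of 9.1-7.8%. Aim 1 predicts a phase difference and also a correlation with level. Requiring both gives 0.9-2.2%.

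**Which estradiol test leads Aim 1.** The Aim 1 paragraph sets up the test as early versus late follicular phase and adds the level as a correlate. Statistical Analyses defines the estradiol term by group and sizes the trial by group, and Expected Outcomes contrasts the two groups. Only the Approach section states Aim 1 by level. The phase-or-level wording in Expected Outcomes concerns adjustment of the endocannabinoid prediction, not the Aim 1 test.

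**The case for a change.** The strongest case for a change is that the missing rule costs almost nothing to supply and its absence leaves room to choose after seeing results. That much stands. Under a full null, taking the best of the THC-session, first-session and mean values raises the error to 11%, 9% or 7% per biomarker at r = 0.4, 0.6 and 0.8. The THC-session value is also a natural reading of a baseline for a THC-induced increase, and its bias can run the other way. With augmentation of -0.3 through the mean level and a common slope of +0.3 at r = 0.6, its slope shrinks to -0.24 + 0.3 x 0.4 = -0.12 with power of 12-23%, against -0.30 and 39-88% for mean plus difference.

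The mean is not a universal protection either. A THC-session change score without the placebo contrast gives false positives of 20.9% on the THC-session value and 16.8% on the mean, if the level correlates 0.3 with the concurrent pre-capsule outcome. The plan's within-subject drug term supplies that contrast. In women given THC first, the second draw also follows exposure: 0.5^(4/1.3) = 0.12, so about 12% of the drug remains at four days by the stated half-life. The mean is then not a pure baseline.

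These points show that each option has its costs. They do not show that the plan has chosen a wrong one.

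**Conclusion.** No change follows. The documents leave the session value for AEA and 2-AG unstated and do not write out the drug-by-moderator term. This is a gap in the detail of the biomarker analyses, and it can be filled sensibly when the model is coded. The aims are plainly about augmentation, so the interaction is implied, and drug is already a within-subject factor.

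The false-positive range of about 6% to 51% needs three things together: use of the THC-session value alone, which the plan does not select; session-to-session variation in the level that drives the outcome equally under THC and placebo; and assumed values of beta, r and rho that the documents do not give. Without any one of the first two, the error is about 5%. At a between-session correlation of 0.9 it is negligible even for the THC-session value (5.3% for a slope of 0.3).

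For Aim 1, making the randomised phase contrast the lead test would largely restate what the plan already says. For the biomarkers, a woman's mean level and her THC-day level answer different questions, and which has more power depends on the unknown mechanism.

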Upon arrival at each session at 12 pm, subjects will complete breath, drug, and pregnancy screens to verify compliance (Alco-Sensor® III, CLIAwaived, Inc. Rapid Drug Test Cup, CLIAwaived, Inc. Pregnancy Urine (Dip-Strip)). Subjects who test positive will be dismissed. Then, pre-capsule heart rate, blood pressure and body temperature will be measured, and subjects will complete subjective questionnaires measuring mood and drug effects (see below). Then a trained and certified research assistant will collect a saliva sample and draw two 5 ml samples of blood to be analyzed for ovarian hormones, estradiol and progesterone, and endocannabinoids, anandamide (AEA) and 2- arachidonoylglycerol (2-AG) (see assay section below). Then they will consume a capsule containing placebo or THC (7.5, 15 mg; see drug section below). Sessions will be run from 12:00 pm to 4:00 pm. Every 30 or 60 min throughout the session, heart rate, blood pressure, and body temperature will

be measured, a saliva sample will be taken and subjective questionnaires assessing mood, the Profile of Mood States (POMS, McNair et al., 1971) and State Anxiety Inventory (STAI, Spielberger et al. 1971), and drug effects, the Addiction Research Center Inventory (ARCI, Haertzen et al. 1963) and the Drug Effects Questionnaire (DEQ, Johanson and Uhlenhuth, 1980; Morean et al. 2013), will be administered (see timeline below).

Measures Physiological: Blood pressure will be recorded at half hour intervals (see timeline below) using portable Omron 10 Series Upper Arm Blood Pressure Monitor to measure cardiovascular effects of the drug. Body temperature will also be measured using a Metene Medical Forehead and Ear Thermometer. An electrocardiogram and thoracic impedance will be measured to examine effects on heart rate, heart rate variability, and respiration. Seven disposable self-adhesive electrodes will be placed on the participant's chest and back to produce a standard lead II configuration for ECG and standard tetrapolar electrode configuration for thoracic impedance. ECG and thoracic impedance measures will be amplified and processed by an integrated Mindware Bionex system (Mindware, Gahanna, OH). These measures will be used to both track the cardiovascular effects of the drug, and ensure participant safety.

Subjective: Participants will complete standardized questionnaires.

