sex-specific cannabis use guidelines, to prevent against THC-induced anxiety, paranoia, and psychosis, and new sex-specific cannabis use disorder treatment options.

Potential problems, Alternative strategies, and Limitations Several problems could arise. First, it may be difficult to recruit qualifying participants in the planned time frame. This seems unlikely since similar inclusion criteria have been used in prior studies within the lab and there has not been significant difficulty recruiting these individuals. But if this is the case, I will increase venues for advertising and identify new online recruitment sources. Second, the differences in responses to THC in females at different phases of their menstrual cycle may be too small to detect with this sample. This is possible, even though we based the sample size on a small effect size. If the findings look promising we would consider increasing our sample size or utilize the data as a pilot for a future study with a larger sample. Third, the two groups of females may differ in pre-capsule measures, such as mood states, cortisol levels, eCB levels, blood pressure or in demographic characteristics such as prior drug use. I will include any of these significant differences between groups as a covariate in the final analyses.

Literature Cited

American Psychiatric Association. (2013). Cautionary statement for forensic use of DSM-5. In *Diagnostic and statistical manual of mental disorders* (5th ed.). doi:10.1176/appi.books .9780890425596.744053

Craft, R. M., & Leitl, M. D. (2008). Gonadal hormone modulation of the behavioral effects of Δ9-tetrahydrocannabinol in male and female rats. *European Journal of Pharmacology*, 578(1), 37–42.

Crean, R. D., Crane, N. A., & Mason, B. J. (2011). An Evidence Based Review of Acute and Long-Term Effects of Cannabis Use on Executive Cognitive Functions. *Journal of Addiction Medicine*, 5(1), 1–8. <https://doi.org/10.1097/ADM.0b013e31820c23fa>

D'Souza, D. C., Ranganathan, M., Braley, G., Gueorguieva, R., Zimolo, Z., Cooper, T., ... Krystal, J. (2008). Blunted Psychotomimetic and Amnestic Effects of Δ-9-Tetrahydrocannabinol in Frequent Users of Cannabis. *Neuropsychopharmacology*, 33(10), 2505–2516. <https://doi.org/10.1038/sj.npp.1301643>

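### The analysis of the two-session counterbalanced design names no session-order term; the likely cost is a modest loss of precision, avoidable almost for free

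*Combined protocol and SAP*

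**What the plan says.** All references are to the combined protocol and SAP.

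- **Design (Approach).** "Subjects will attend two four-hour experimental sessions in which they receive THC (15 mg THC) or placebo in counterbalanced order under double blind conditions". Within each phase group (EFG or LFG, 30 women each) this is a two-period crossover.
- **Model (Statistical Analyses; the same list is under Aim 3).** "Our independent variables include within-subjects drug dose and between subjects estradiol (EFG or LFG), AEA and 2-AG levels". Anxiety is the mediator; heart rate, blood pressure and salivary cortisol are the outcomes. Session time in this model means the time points within a visit, not first versus second visit.
- **Other covariates (Potential problems, Alternative strategies, and Limitations).** "I will include any of these significant differences between groups as a covariate in the final analyses". The differences meant are those between EFG and LFG in pre-capsule or demographic measures, so this rule does not bring session order in.
- **Screening (Orientation Session; Experimental Session Timeline).** Women "must pass urine tests on the days of their experimental sessions for recent drug use including cannabis". The screen is repeated on arrival at each session, and "Subjects who test positive will be dismissed". No exception is written for a positive caused by THC given at session 1.
- **Gap between sessions (Experimental Session Timeline; Aim 1 gives the same minimum).** "Therefore sessions will be scheduled with a minimum of 4 days to allow for washout". No maximum is set, and the text does not require both sessions to fall in one cycle.

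**The concern.** A first visit and a second visit can differ for reasons unrelated to drug, such as novelty, practice or familiarity with the laboratory. Anxiety and cortisol are plausible places for such a difference, although the documents report none. The trial counterbalances order, so order is a design factor, but the written model does not use it.

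Two consequences follow, of unequal weight.

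1. **Precision (main).** With balanced sequences, an order effect pushes the THC-minus-placebo difference down in THC-first women and up by the same amount in placebo-first women. The mean is unaffected, but the spread counts as residual error. The THC-placebo contrast, on which Aim 3 rests, and the drug-by-phase contrast of Aim 1 are both estimated less precisely than they need be. The plan targets a small effect with 60 women.
2. **Bias (secondary).** If one sequence loses more women than the other, part of the order effect enters the THC-placebo contrast. The session-2 screen is one route: only a THC-first woman can be positive at session 2 because of study drug. Drug-by-phase is affected only if that imbalance differs between EFG and LFG.

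**Working it through.** **Figures in the plan.** The plan gives no order effect, between-session correlation or loss rate, so there is no stated figure to reproduce. From the documents: 60 women, 30 per phase group, two sessions, counterbalanced order. I take counterbalancing to mean 15 women per sequence in each group.

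**Assumptions.** One response summary per session with SD 1. Order effect (session 2 minus session 1) δ = 0.3, range 0.1-0.5. Between-session correlation ρ = 0.5, range 0.3-0.7. Share of THC-first women lost at session 2, q = 0, 0.1 or 0.25.

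**Step 1. Precision with no loss.** The THC-minus-placebo difference has variance 2(1−ρ) within a sequence. Its mean is shifted by −δ in THC-first women and +δ in placebo-first women. With no order term, this adds δ² × 60/58 to the residual variance (60 women, 58 df after fitting phase group):

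SE ratio = √(1 + δ² × (60/58) / [2(1−ρ)])

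At δ = 0.3 and ρ = 0.5: √(1 + 0.09 × 1.0345 / 1.0) = √1.0931 = 1.046.

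| δ | ρ = 0.3 | ρ = 0.5 | ρ = 0.7 |
|---|---|---|---|
| 0.1 | 1.004 | 1.005 | 1.009 |
| 0.3 | 1.033 | 1.046 | 1.075 |
| 0.5 | 1.089 | 1.122 | 1.196 |

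The ratio is the same for THC-placebo and drug-by-phase. At δ = 0.3, ρ = 0.5, the lost information is worth 60 × (1 − 1/1.09) = 5.0 women. Simulation of 20,000 trials also gives 1.046.

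**Step 2. Direction of the error.** The residual is inflated while the estimate stays unbiased, so the tests are conservative. At δ = 0.3, ρ = 0.5 and no loss, the simulated type I error for THC-placebo is about 3.9% against a nominal 5%.

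**Step 3. Bias if THC-first women are lost.** With no order term, THC-placebo carries this fraction of the order effect:

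- Completers only: q/(2−q), which is 0.053 at q = 0.1 and 0.143 at q = 0.25.
- Mixed model keeping session-1 data: [(1+ρ)/2] × q/(2−q), which is 0.034-0.045 at q = 0.1 and 0.093-0.121 at q = 0.25 over ρ = 0.3-0.7.

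At δ = 0.3 the completer bias is 0.016 and 0.043 SD. The mixed-model bias at ρ = 0.5 is 0.012 and 0.032 SD. In whole women, losing 4 of 15 in each THC-first sequence gives (15−11)/(15+11) × 0.3 = 0.046 SD. The range is therefore about 0.01-0.05 SD. The standard error of THC-placebo with 60 women at ρ = 0.5 is √(1/60) = 0.129, or about 0.14 after inflation and loss. Type I error stays near 5% (about 4.0% at q = 0.1 and 5.0% at q = 0.25 for δ = 0.3, ρ = 0.5).

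Drug-by-phase carries nothing if q is equal in both groups. If q is 0.1 in one and 0.25 in the other, completers carry 0.143 − 0.053 = 0.090 of the order effect, or 0.027 SD at δ = 0.3. Its standard error before loss is √(1/30 + 1/30) = 0.258.

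**Step 4. Effect of the fix.** With order and order by phase in the model, the order component is zero in every case above. Order alone is not always enough: if the order effect is 1 in the group with q = 0.1 and 1.5 in the group with q = 0.25, it leaves 0.037 in drug-by-phase, and adding order by phase removes it. If there is no order effect, the cost is a critical t of 2.0032 (56 df) instead of 2.0017 (58 df), a rise of 0.08%.

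**The case against.** **The list of model terms is not closed.** It is introduced as what the variables include, so an order term may be intended. That is fair, but an unwritten term is not pre-specified.

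**The order effect may be small, or may cancel.** Each session has its own pre-capsule baseline, and the hypotheses concern increases after THC. If outcomes are analysed as change from that baseline, an order effect that shifts a whole session equally drops out; only one acting on the within-session response remains. This stands. The plan does not fix how baseline enters, so the point survives, but the sizes above apply only to an order effect of that second kind.

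**The omission does not produce false positives.** This also stands within the ranges used. Bias and inflated standard error pull against each other: over the whole grid, type I error for THC-placebo runs from 1.9% to 5.6%, and for drug-by-phase it stays at about 5% or below.

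**A stronger reading to resist.** A reader might infer that the screen will systematically remove THC-first women and so bias the drug effect. The half-life quoted in the plan, 1.3 days, leaves about 12% of the drug after four days (0.5^(4/1.3)), and women are advised to abstain for one to two weeks to pass the screen. Within one cycle, no pair of LFG test days at least four days apart reaches seven days. These facts make a positive conceivable but do not establish one. The abstinence advice concerns women's own use, not one 15 mg oral dose. The documents give no assay cutoff or positivity rate. Four days is only a minimum, and separate cycles are not excluded. Dismissal is undefined and may mean only being sent home that day; if the woman is rebooked, loss is near zero.

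**Conclusion.** The point holds as a modest one about precision. The trial counterbalances session order, but no section puts order in the model. If an order effect on the within-session response exists, omitting it widens the standard errors of the THC-placebo and drug-by-phase contrasts by about 3-7% at 0.3 SD, under 1% at 0.1 SD and 9-20% at 0.5 SD. With balanced sequences the tests are slightly conservative.

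The documents do not support a claim of material bias. Loss of THC-first women through the session-2 screen is possible but unquantified. Even at 25% loss and a 0.3 SD order effect, the shift is at most about 0.05 SD against a standard error near 0.14, and it may be zero. The Aim 1 contrast is touched only if loss differs by phase.

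Every size rests on assumed values for the order effect, the between-session correlation and the loss rate. This is an improvement worth considering because it costs almost nothing, not a flaw that threatens the conclusions.

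**What to change.** In Statistical Analyses:

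1. Add session order (first or second session) and order by phase group as fixed effects, both in the anxiety (mediator) equation and in the heart rate, blood pressure and cortisol equations.
2. State that session-1 data of every randomised woman are kept, whether or not session 2 takes place.
3. Report session-2 losses and delays by sequence and phase group.

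The order terms remove bias due to the order effect. They do not remove selection if women lost at session 2 differ in THC clearance or response; the report by sequence lets readers judge that.

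**Cost.** About three sentences, no added participants and two degrees of freedom.

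**Optional (Experimental Session Timeline).** Say what dismissal means, and rebook a woman whose only session-2 positive is for cannabinoids within her assigned phase window, in a later cycle if needed. This would cost a repeat visit and a longer gap between sessions. Staff who see a cannabinoid positive at session 2 may guess the session-1 capsule, but that is already so under the current rule.
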